**Table 8. Operational Definitions of Exposure**

Exposure group name(s)	Details	Washout window	Assessment Window	Care Setting 	Code Type	Diagnosis position 	Applied to study populations:	Incident with respect to...	Measurement characteristics/ validation	Source of algorithm
Antidepressants (classes)	Preliminary code list provided in Table 7	[-365, ID]	Calendar year	Primary and secondary care	RxNorm	n/a	All patients with newly diagnosed MDD present in the database during the study period.	Previous use of antidepressants of interest	n/a	n/a
Psycholeptics (classes)	Preliminary code list provided in Table 7	[-365, ID]	Calendar year	Primary and secondary care	RxNorm	n/a	All patients with newly diagnosed MDD present in the database during the study period and being treated with an antidepressant.	Previous use of psycholeptics of interest	n/a	n/a

	D2.2.3 –Study Protocol for P2 C1-008	
	Author(s): [name], [name]	Version: v3.1 – Final
		Dissemination level: public

 IP = inpatient, OP = outpatient, ED = emergency department, OT = other, n/a = not applicable;  Specify whether a diagnosis code is required to be in the primary position (main reason for encounter)

	D2.2.3 –Study Protocol for P2 C1-008	
	Author(s): [name], [name]	Version: v3.0 – Revised
	Dissemination level: Confidential	

### 8.6.2. Outcomes

This study will examine the following four primary outcomes of interest.

- Treatment Initiation

Initiation of treatments will be assessed within a window of 4, 6, 8, 12, and 24 weeks following diagnosis. In relation to the outcome, a predefined list of MDD treatments will be compiled to address Objectives 1 and 3. MDD treatments will include NSRIs, SSRIs, other antidepressants, and concomitant drugs of interest (Psycholeptics - N05A, N05B, and N05C) as listed in Table 7.

- Treatment Switching

Switching of treatments will be assessed within a window of 4, 6, 8, 12, and 24 weeks following treatment initiation. In relation to the outcome, a predefined list of MDD treatments will be compiled to address Objectives 1 and 3. MDD treatments will include NSRIs, SSRIs, other antidepressants, and concomitant drugs of interest (Psycholeptics - N05A, N05B, and N05C) as listed in Table 7.

- Treatment Discontinuation

Discontinuation of treatments will be assessed within a window of 4, 6, 8, 12, and 24 weeks following treatment initiation. In relation to the outcome, a predefined list of MDD treatments will be compiled to address Objectives 1 and 3. MDD treatments will include NSRIs, SSRIs, other antidepressants, and concomitant drugs of interest (Psycholeptics - N05A, N05B, and N05C) as listed in Table 7.

	D2.2.3 –Study Protocol for P2 C1-008	
	Author(s): [name], [name]	Version: v3.0 – Revised
	Dissemination level: Confidential	

**Table 9. Operational Definitions of Outcome**

Outcome name	Details	Primary outcome?	Type of outcome?	Wahout window	Care Setting	Code Type	Diagnosis Position	Applied to study populations	Measurement characteristics/validation	Source of algorithm
Treatment initiation	Preliminary code lists provided in Table 7	Yes	Binary: Counts and percentages	365 days as incident use only	IP and OP care	RxNorm	N/A	All patients with incident MDD	N/A	N/A
Treatment Switching	Preliminary code lists provided in Table 7	Yes	Binary: Counts and percentages	365 days as incident use only	IP and OP care	RxNorm	N/A	All patients with incident MDD undergoing treatment	N/A	N/A
Treatment Discontinuation	Preliminary code lists provided in Table 7	Yes	Binary: Counts and percentages	365 days as incident use only	IP and OP care	RxNorm	N/A	All patients with incident MDD undergoing treatment	N/A	N/A

IP = inpatient, OP = outpatient, n/a = not applicable

	D2.2.3 –Study Protocol for P2 C1-008	
	Author(s): [name], [name]	Version: v3.0 – Revised
		Dissemination level: Confidential

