### Data analyses

Objective 1: The number and percentage of patients with newly diagnosed MDD initiating treatment with antidepressants will be estimated at 4, 6, 8, 12, and 24 weeks after date of new MDD diagnosis; and the number and percentage of those discontinuing and switching treatment at 4, 6, 8, 12, and 24 weeks following start of antidepressant therapy. They will be reported in tabular form as absolute numbers as well as

	D2.2.3 –Study Protocol for P2 C1-008	
	Author(s): [name], [name]	Version: v3.1 – Final
		Dissemination level: public

proportions, and depicted using Sunburst plots and Sankey diagrams. The statistical analyses will be performed based on OMOP-CDM mapped data using the “TreatmentPatterns” R package.

Objective 2: The duration (mean, median, quantiles 25% and 75%, minimum and maximum) of antidepressant use in patients with newly diagnosed MDD during the first treatment era will be estimated. The index date will be determined as the date of the first prescription of the specific antidepressant class for each individual. Statistical analyses will be conducted using the "DrugUtilization" R package based on OMOP-CDM mapped data.

Objective 3: The number and percentage of patients with newly diagnosed MDD initiating, switching, or discontinuing treatment with psycholeptics) will be estimated at 4, 6, 8, 12, and 24 weeks after the date of treatment initiation with antidepressants; and at 4, 6, 8, 12, and 24 weeks after starting psycholeptics (for switching or discontinuing treatment). This will be reported in tabular form as absolute numbers as well as proportions and depicted using Sunburst plots and Sankey diagrams. The statistical analyses will be performed based on OMOP-CDM mapped data using the “TreatmentPatterns” R package.

For all analyses, results will be reported with a minimum cell count of 5, and any counts smaller than 5 will be reported as <5 to ensure privacy and confidentiality.

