### **Study objectives**

1. To examine the proportion of patients with newly diagnosed major depressive disorder who start treatment with antidepressants (NSRIs, SSRIs, or other anti-depressants), as well as those who switch or discontinue treatment by specific timepoints (4, 6, 8, 12, and 24 weeks after treatment initiation), stratified by age, sex, and country/database during the study period (2013 - 2022).
2. To estimate the duration of antidepressant use in patients with newly diagnosed major depressive disorder who initiate treatment with antidepressants (NSRIs, SSRIs, or other antidepressants), stratified by age, sex, and country/database during the study period (2013 - 2022).
3. To assess the proportions of patients with newly diagnosed major depressive disorder who initiate, switch, or discontinue treatment with psycholeptics (antipsychotics, anxiolytics, hypnotics, and sedatives) by specific timepoints (4, 6, 8, 12, and 24 weeks) after starting antidepressant therapy, stratified by age, sex, and country/database during the study period (2013 - 2022).

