**Table 2: Primary and secondary research questions and objective**

#### **A. Primary research question and objectives**

Objective:	To examine the proportion of patients with newly diagnosed major depressive disorder who start treatment with antidepressants (NSRIs, SSRIs, or other anti-depressants) and psycholeptics (antipsychotics, anxiolytics, hypnotics and sedatives) , and of those the proportion who switch or discontinue treatment by specific timepoints (4, 6, 8, 12, and 24 weeks) after treatment initiation, stratified by age group, sex, and country/database during the study period (2013 - 2022).
Hypothesis:	Not applicable
Population (mention key inclusion-exclusion criteria):	All patients with newly diagnosed major depressive disorder who are aged 12 years and above in the respective databases from 2013 to 2022 (or the latest available date if earlier), with a minimum of 1 year of data visibility before their diagnosis, and no previous record of major depressive disorder in the year preceding their diagnosis.
Exposure:	
 
• Antidepressants: 
 
1. Non-selective monoamine reuptake inhibitors
 
2. Selective serotonin reuptake inhibitors
 
3. Other Antidepressants (excluding esketamine and 14ypericin herba)
 
 
 
• Psycholeptics: 
 
1. Antipsychotics
 
2. Anxiolytics
 
 
 

	D2.2.3 –Study Protocol for P2 C1-008	
	Author(s): [name], [name]	Version: v3.1 – Final
	Dissemination level: public	

	3. Hypnotics and sedatives
Comparator:	None
Outcome:	Treatment initiation, treatment discontinuation and treatment switch.
Time (when follow up begins and ends):	Follow-up will start on the date of MDD diagnosis (index date) until the earliest of loss to follow-up, end of data availability or death, or end of study period (31st December 2022).
Setting:	Inpatient and outpatient setting using data from the following 5 data sources: CPRD GOLD (UK), IQVIA DA Germany (Germany), IMASIS (Spain), IPCI (the Netherlands) and SIDIAP (Spain).
Main measure of effect:	Proportions (%), patient level characterisation to assess the use patterns of the respective drugs of interest.

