### 8.4 Follow-up

Patient-level characterisation: study participants will be followed from the date of MDD diagnosis (index date) until the earliest of loss to follow-up, end of data availability, death, or end of study period (31st December 2022). Additionally:

- To assess the proportions of patients with newly diagnosed MDD initiating antidepressant therapy, incident MDD cases will be followed from the date of MDD diagnosis (index date) until the first prescription of the antidepressant class of interest, up to 24 weeks following MDD diagnosis.
- To assess the proportions of patients with newly diagnosed MDD switching or discontinuing specific antidepressant therapy, incident MDD cases on antidepressant therapy will be followed from the date of the first prescription of the specific antidepressant class of interest up to the date of specific intervals (4, 6, 8, 12, and 24 weeks) after starting antidepressant therapy.
- To assess the proportions of patients with newly diagnosed MDD starting, switching and discontinuing concomitant therapy with psycholeptics, incident MDD cases on antidepressant therapy will be followed from the date of the first prescription of the specific antidepressant class of interest up to the date of specific intervals (4, 6, 8, 12, and 24 weeks) after starting antidepressant therapy.

Patient-level utilization of antidepressants: study participants will be followed up from the date of incident prescription and/or dispensation of antidepressant class of interest (index date) until the earliest of loss to follow-up, end of data availability, death, or end of study period (31st December 2022).

	D2.2.3 –Study Protocol for P2 C1-008	
	Author(s): [name], [name]	Version: v3.0 – Revised
	Dissemination level: Confidential	

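### Psycholeptic initiation, a primary outcome, has two conflicting denominators and two conflicting start dates

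*Protocol*

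**What the plan says.** One group of sections uses all incident MDD patients and the diagnosis date:

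- Section 8.6.2 sets the timing of the initiation outcome: "Initiation of treatments will be assessed within a window of 4, 6, 8, 12, and 24 weeks following diagnosis". The treatments it covers, for Objectives 1 and 3 alike, include "concomitant drugs of interest (Psycholeptics - N05A, N05B, and N05C) as listed in Table 7".
- Table 9 has one row for treatment initiation, flagged as primary, with the population "All patients with incident MDD". Its rows for switching and discontinuation add a restriction to patients undergoing treatment; the initiation row does not.
- Table 2A puts antidepressants and psycholeptics into one objective, with all newly diagnosed patients as the population and follow-up from the diagnosis date.
- Section 8.8.3 describes receipt of every treatment listed in section 8.6.1, psycholeptics included, at the index date and at fixed weeks after it. Section 8.4 sets the index date for this part of the study at MDD diagnosis.

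A second group uses antidepressant-treated patients or the antidepressant start date:

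- Table 8, psycholeptics row: "All patients with newly diagnosed MDD present in the database during the study period and being treated with an antidepressant".
- Section 8.4, third bullet: "To assess the proportions of patients with newly diagnosed MDD starting, switching and discontinuing concomitant therapy with psycholeptics, incident MDD cases on antidepressant therapy" are followed from the first antidepressant prescription.
- Objective 3 (Abstract and section 7) sets its timepoints after the start of antidepressant therapy. The Abstract's Data analyses text for that objective likewise gives "weeks after the date of treatment initiation with antidepressants".

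**The concern.** The study is meant to show whether intercurrent events occur as often in practice as in trials. The Abstract (Rationale and Background) defines such events as occurring after treatment has begun. A psycholeptic started by a patient who never takes an antidepressant is therefore not an intercurrent event of antidepressant treatment, nor is one started between diagnosis and the first antidepressant. Section 8.6.2 and Table 9 count both; Table 8 and section 8.4 count neither. Two programmers working from the same Protocol could produce different tables for a primary outcome. The gap between those tables depends on how many patients start an antidepressant. That share can differ by database, age group and sex, which are the planned strata, so comparisons between strata could be affected as well as the overall level.

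**Working it through.** The Protocol gives no expected percentage for these outcomes, so there is no figure to reproduce. The check compares the definitions and then sizes the gap under stated assumptions.

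**Step 1: definitions compared.**

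| | Section 8.6.2, Table 9, Table 2A, section 8.8.3 | Table 8, section 8.4 (third bullet), Objective 3 |
|---|---|---|
| Denominator | all incident MDD (Table 9, Table 2A) | antidepressant-treated incident MDD (Table 8, section 8.4) |
| Time zero | MDD diagnosis | antidepressant start (section 8.4, Objective 3) |
| Psycholeptic without any antidepressant | counted | not counted |
| Psycholeptic between diagnosis and first antidepressant | counted | not counted |

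Denominator, numerator and clock all differ.

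**Step 2: effect of the denominator and numerator.** Let f be the share of incident MDD patients who start an antidepressant, p1 the psycholeptic initiation share in starters, and p0 that share in non-starters. All three are assumptions.

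- Over all incident MDD: p_all = f × p1 + (1 − f) × p0
- Over starters: p1
- Difference: p_all − p1 = (1 − f) × (p0 − p1)

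With f = 60%, p1 = 15%, p0 = 10%: p_all = 0.6 × 15% + 0.4 × 10% = 9% + 4% = 13%, against 15% in starters. The difference is 0.4 × (−5) = −2 percentage points.

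The sign follows p0 − p1. If p0 were 20%, p_all would be 0.6 × 15% + 0.4 × 20% = 9% + 8% = 17%, which is above 15%.

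**Step 3: range.** With p1 fixed at an assumed 20% and p0 varied from 0% to 30%:

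- f = 0.3: p_all runs from 0.3 × 20% = 6% to 6% + 0.7 × 30% = 27%
- f = 0.5: from 0.5 × 20% = 10% to 10% + 0.5 × 30% = 25%
- f = 0.9: from 0.9 × 20% = 18% to 18% + 0.1 × 30% = 21%

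The two readings agree only if p0 = p1, or as f approaches 1.

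**Step 4: effect of the clock.** Steps 2 and 3 hold time zero constant, but the Protocol's two readings do not. As an illustration, take a patient who starts an antidepressant 8 weeks after diagnosis. A 12-week window from diagnosis holds 8 weeks before treatment and only 12 − 8 = 4 weeks on it. A 12-week window from antidepressant start holds 12 weeks after treatment began. The documents do not give the distribution of time from diagnosis to first antidepressant, so this effect cannot be quantified.

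**The case against.** The best defence is that the specific text should govern the general. Every passage devoted to psycholeptics alone (Table 8, the third bullet of section 8.4, Objective 3) points to antidepressant-treated patients or antidepressant start, and section 8.6.2 itself calls these drugs concomitant. On this view Table 9's initiation row is shorthand serving Objectives 1 and 3 together, and Table 2A is a merged summary. This shows which reading was probably intended, but it does not remove the conflict. Table 9 is the operational definition of the outcomes, and it does vary the population by row, so the wider population for initiation looks deliberate. Sections 8.6.2 and 8.8.3 also carry the diagnosis-based clock, and no order of precedence is given.

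It is also fair to say that the illustrated gap is modest, at 2 points, that its direction is not fixed, and that every rate is assumed. All of that stands.

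Two stronger readings are tempting and should be resisted. First, a reader might infer that antidepressant switching and discontinuation also have conflicting denominators, because Objective 1 in section 7 says "as well as those who switch or discontinue treatment by specific timepoints (4, 6, 8, 12, and 24 weeks after treatment initiation" where Table 2A says "and of those the proportion who switch or discontinue treatment by specific timepoints (4, 6, 8, 12, and 24 weeks) after treatment initiation". The documents do not support that as an analysis conflict. The Abstract and Table 2A use starters, Table 9's own rows for these outcomes require treatment, section 8.4 follows patients on antidepressants from first prescription, and section 8.6.2 times the windows from treatment initiation. Even the section 7 sentence sets its timepoints after treatment initiation. It is loose wording in one objective, and no analysis section prescribes an all-MDD denominator for these outcomes.

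Second, a reader might suppose that the all-MDD psycholeptic figure is simply the starters' rate multiplied by the initiation share. Table 9 does not define it that way: events in non-starters are counted too, so the second term of the formula must be kept.

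**Conclusion.** The point holds for psycholeptic initiation. The Protocol defines this primary outcome over two populations and from two start dates, and one of the two versions counts prescriptions that fall outside the Protocol's own definition of an intercurrent event. At an assumed 60% antidepressant initiation, with psycholeptic initiation of 15% in starters and 10% in non-starters, the reported percentage would be 13% instead of 15%, leaving aside the different clock. Neither the size nor the sign can be fixed from the documents: the gap grows as fewer patients start an antidepressant, and it reverses if non-starters have the higher psycholeptic rate. The point does not extend to antidepressant switching and discontinuation, where section 7 needs only a wording correction.

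**What to change.** 1. In Table 9 and section 8.6.2, split treatment initiation into two outcomes: (a) antidepressant initiation among all patients with incident MDD, counted from diagnosis; (b) psycholeptic initiation among patients with incident MDD who have started an antidepressant, counted from antidepressant start. Changing Table 9 alone would leave the diagnosis-based clock in section 8.6.2.
2. In Table 2A, separate psycholeptics from the antidepressant objective, with their own population and follow-up start to match (b).
3. In section 8.8.3, state which time zero applies to which drug group in place of a single index date.
4. Wording only: in section 7, Objective 1, adopt the Table 2A phrasing so that switching and discontinuation are explicitly proportions of those who started treatment.

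This is the reading that Table 8, section 8.4 and Objective 3 already take. The cost is a few lines of text, with no additional data and no additional analysis. Section 5 schedules creation and execution of the analytical code for the same month, so the definition needs to be settled before the code is written.

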### 8.6.3. Other covariates, including confounders, effect modifiers and other variables (where relevant)

Age at MDD diagnosis will be described. The following age grouping will be used: 12-17, 18 – 44, 45 – 64, and 65 years and above. The sex (male/ female) of study participants will also be identified.

All co-morbidities and concomitant-medications recorded prior (any time prior to the ID, 365 to 31 days prior to the ID and -30 to 1 day before ID) will be used for large-scale patient characterisation, identified as concept/code and descendants.

In addition, the distribution of the initial quantity of the antidepressant of interest at time of first prescribing will be provided. This will be presented by minimum, P25, median, P75 and maximum.

**Table 10. Operational Definitions of Covariates**

Characteristic	Details	Type of variable	Assessment window	Care Settings 	Code Type	Diagnosis Position 	Applied to study populations:	Measurement characteristic/ validation	Source for algorithms
Large-scale summary characteristics of new users	Large-scale patient-level characterization with regard to baseline covariates	Binary/categorical: Counts and percentages	Any time prior to the ID, 365 to 31 days prior to the ID and -30 to 1 day before ID	Primary and secondary care	RxNorm	n/a	Persons with new use during the study period	n/a	n/a
Initial quantity of antidepressant of interest	Characterisation	Min, P25, median, P75, max	At Index date (date of first prescribing of the antidepressant of interest)	Primary and secondary care	RxNorm	n/a	Persons with new use during the study period	n/a	n/a

 ID = index date, IP = inpatient, OP = outpatient, ED = emergency department, OT = other, n/a = not applicable

 Specify whether a diagnosis code is required to be in the primary position (main reason for encounter)

	D2.2.3 –Study Protocol for P2 C1-008	
	Author(s): [name], [name]	Version: v3.0 – Revised
	Dissemination level: Confidential	

## 8.7 Study size

A formal sample size calculation was not undertaken for this descriptive study, given that our main objective is to summarise the characteristics and utilization patterns of antidepressants and psycholeptics in newly diagnosed MDD patients. Based on a preliminary feasibility assessment, the expected number of patients with MDD records in the included databases for this study will be approximately 380,000.

## 8.8 Data analysis

**Table 11.** Description of Study Types and Type of analysis

STUDY TYPE	STUDY CLASSIFICATION	TYPE OF ANALYSIS
Disease Epidemiology - Patient Level Characterisation	Off-the-shelf (C1)	
 
- Percentage of patients initiating treatment with specific antidepressants or psycholeptics
 
- Percentage of patients switching treatment to specific antidepressants or psycholeptics
 
- Percentage of patients discontinuing treatment with specific antidepressants or psycholeptics
 

Patient Level DUS	Off-the-shelf (C1)	
 
- Estimation of the mean, median, 25th percentile, 75th percentile, minimum, and maximum durations of antidepressant use.
 
- Estimation of the median, 25th percentile, 75th percentile, minimum, and maximum of the drug quantity at first prescription of the antidepressant of interest
 

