#### Patient-level characterisation: Treatment initiation, switching, and discontinuation

To characterise treatment of MDD, the number and percentages of patients receiving each of a pre-specified list of MDD treatments (as listed in section 8.6.1) will be described at index date, and 4, 6, 8, 12, and 24 weeks post index date. The criteria for treatment switching and discontinuation will be based on the options currently available in the standard analytical tools that will be used in this project, specifically, the “TreatmentPattern” R package. This analysis will produce sunburst plots and Sankey diagrams to describe treatment initiation, switching and discontinuation over time (objectives 1 and 3).

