**Figure 3. Parameters in TreatmentPatterns package (25)**

The following parameters will be defined in this study.

Parameters	Values (days)	Description
periodPriorToIndex	0	Number of days prior to the index date of the target cohort
minEraDuration	0	Minimum time an event era should last to be included in analysis
eraCollapseSize	7	Window of time between which two eras of the same event cohort are collapsed into one era
combinationWindow	7	Window of time two event cohorts need to overlap to be considered a combination treatment
minPostCombinationDuration	7	Minimum time an event era before or after a generated combination treatment should last to be included in analysis
filterTreatments	All	Select all treatments including first time occurrences and sequential repeated treatments
maxPathLength	5	Maximum number of steps included in treatment pathway

For all continuous variables, summary descriptive statistics will be reported: median and interquartile interval will be reported. For all categorical analyses, counts and percentages will be reported. A minimum cell count of 5 will be used when reporting results, with any smaller counts reported as “<5”. All analyses will be

	D2.2.3 –Study Protocol for P2 C1-008	
	Author(s): [name], [name]	Version: v3.1 – Final
		Dissemination level: public

reported by country/database, overall and stratified by age and sex when possible (minimum cell count reached).

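### Switching and discontinuation are defined over one list mixing antidepressants with psycholeptics, against the protocol's own separate objectives, so stopping an antidepressant and starting a psycholeptic can count as a switch

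*Protocol*

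**What the plan says.** Four places in the protocol put the two drug groups together.

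- **Section 8.6.2 (Outcomes).** Under initiation, switching and discontinuation alike, "a predefined list of MDD treatments will be compiled to address Objectives 1 and 3", and "MDD treatments will include NSRIs, SSRIs, other antidepressants, and concomitant drugs of interest (Psycholeptics - N05A, N05B, and N05C) as listed in Table 7".
- **Table 11 (section 8.8).** The switching measure is "Percentage of patients switching treatment to specific antidepressants or psycholeptics". No class of origin is given, and nothing confines a switch to one therapeutic group.
- **Section 8.8.3.** The treatments to be described are those of section 8.6.1, whose Table 7 holds all six classes. A single analysis is said to serve Objectives 1 and 3. "The criteria for treatment switching and discontinuation will be based on the options currently available in the standard analytical tools", namely the TreatmentPatterns package.
- **Table 2, part A.** Objectives 1 and 3 are merged into one primary objective covering patients who start either drug group, "and of those the proportion who switch or discontinue treatment by specific timepoints (4, 6, 8, 12, and 24 weeks) after treatment initiation".

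Other places keep the groups apart. In the abstract and section 7, Objective 1 concerns antidepressants and Objective 3 psycholeptics after antidepressant initiation. The abstract's data analysis paragraph describes them as two analyses. Section 8.4 has one follow-up rule for antidepressant switching and stopping and another for psycholeptics, which it calls concomitant therapy. Table 7 also labels psycholeptics as concomitant drugs.

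**The concern.** The rationale in the abstract gives treatment discontinuation, a switch to alternative therapy and a change in background or concomitant therapy (sleep aids are its example) as distinct intercurrent events. The study is meant to show how often such events occur in practice, so that trial results can be judged against those rates.

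A patient who stops an SSRI and starts an anxiolytic has discontinued the antidepressant and changed concomitant therapy. If the six classes are treated as interchangeable treatments, the same path can read as a switch. The reported proportions would then no longer separate the events of interest. Any such distortion would depend on how often psycholeptics are prescribed locally, and the five databases are to be reported side by side without pooling.

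**Working it through.** The plan has no figure of its own to reproduce here: it is descriptive and states no expected switching or discontinuation proportion. The check is a comparison of the text, followed by a bound.

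**1. Is one list used for both objectives?** Yes. Section 8.6.2 repeats the same six-class list under all three outcomes and ties it to Objectives 1 and 3 jointly. Section 8.8.3 reaches the same six classes through Table 7.

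**2. Is a psycholeptic a permitted switch destination?** Yes, on the wording of Table 11. No passage limits an antidepressant switch to another antidepressant class.

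**3. Does the package parameter table settle it?** No. It sets time windows, an occurrence filter and a maximum path length. It does not say which drug groups enter a run together.

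**4. How are the possible sequences classified?**

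| Sequence | What the protocol supports |
|---|---|
| SSRI ends, anxiolytic then starts | Can be a switch under Table 11; whether it is also an antidepressant discontinuation is not stated |
| SSRI and anxiolytic overlap enough to form a combination, then anxiolytic alone | The label for the last step is not stated |
| Hypnotic added to a continuing SSRI with enough overlap | A combination; no text calls it a switch |

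The second and third rows turn on combinationWindow, set at 7 days ("Window of time two event cohorts need to overlap to be considered a combination treatment"). The second also involves minPostCombinationDuration, again 7 days ("Minimum time an event era before or after a generated combination treatment should last to be included in analysis").

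**5. Bound on the shift at a given timepoint.** Let D be the true proportion of antidepressant initiators who have stopped all antidepressants, and q the share of those stoppers who start a psycholeptic. If every such patient is counted as a switcher and not as a discontinuer:

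understatement of discontinuation = overstatement of switching = D x q

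The protocol gives neither D nor q. With assumed values:

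- D = 20%, q = 10%: 0.20 x 0.10 = 2 percentage points
- D = 30%, q = 20%: 0.30 x 0.20 = 6 percentage points
- D = 40%, q = 10%, 30% or 50%: 4, 12 or 20 percentage points
- D = 50%, q = 40%: 0.50 x 0.40 = 20 percentage points

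Each result is an upper bound for its inputs, because it supposes that all such patients are reclassified. If they are counted under both headings, discontinuation is unaffected but antidepressant switching is still inflated.

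**The case against.** The strongest reply is that the list in section 8.6.2 only names the drugs covered by two objectives. It does not prescribe one pathway run, and separate runs would fit the abstract and section 8.4. The three lines of Table 11 may be shorthand, to be read separately for each group. The third line counts patients who discontinue specific antidepressants or psycholeptics, so someone who stops an SSRI could be counted there whatever follows. The package settings might also be left to the study code or an analysis plan.

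Much of this stands. A reader might infer that such a stop is necessarily recorded as a switch and never as a discontinuation. The documents do not support that: nothing makes the two outcomes mutually exclusive, and the criteria are deferred to the package. A reader might also extend the point to patients already taking a psycholeptic when they stop. That is weaker still, because the label for a step from combination to psycholeptic alone is not stated, and the 365-day incident-use washout in Tables 8 and 9 may exclude prevalent psycholeptic users.

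The reply does not remove the contradiction. The only statement of which drugs the switching and discontinuation outcomes cover is the mixed list, and section 8.8.3 describes one analysis of it for both objectives. This is not detail left for later: the protocol fixes the list in its primary outcome definitions, at odds with its own objectives. A drug class called concomitant cannot also be a switch destination for the main drug without a rule saying when.

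**Conclusion.** The point holds as an internal contradiction with an unresolved classification. Section 8.6.2, Table 11, section 8.8.3 and part A of Table 2 apply switching and discontinuation to one mixed list, while Objectives 1 and 3, the abstract's analysis plan and section 8.4 separate the groups. Taken literally, the outcome definition allows an antidepressant stop followed by a new psycholeptic to be counted as a switch, and leaves open whether it is also a discontinuation.

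The size cannot be derived from the protocol. The bound is D x q; the illustrative values above span 2 to 20 percentage points and rest wholly on assumed inputs and on complete reclassification. That distortion would differ between databases follows only if psycholeptic use among stoppers differs, and the protocol gives no figure for that. The correction should be made because it concerns primary outcomes and is cheap.

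**What to change.** Align part A of Table 2, section 8.6.2, Table 11 and section 8.8.3 with the abstract's data analysis paragraph and section 8.4.

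- **Objective 1.** Use N06AA, N06AB and N06AX (with the stated exclusions) as the only event cohorts. Count a switch only when the move is to another antidepressant class. Count discontinuation as the end of antidepressant exposure, regardless of psycholeptic use.
- **Objective 3.** Run N05A, N05B and N05C as a separate pathway in a cohort that starts at antidepressant initiation.
- **Six-class pathways.** If wanted, keep them for sunburst and Sankey plots only, not for the reported proportions.

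The cost is protocol wording and one extra TreatmentPatterns run per database. No new data are needed.
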